Figure 1 – Experimental procedure for one arm of the cross-over design. Both arms of the design will be similar. The only difference will be the NIBS intervention). A three-week break will separate Session 6 from Arm 1 to Session 1 of Arm 2. Sessions 1 and 6 are expected to take ~2.5 hours to complete. Sessions 2 thru 5 are expected to take ~1.25 hours to complete. SR task – serial reaching task. PANAS - Positive and Negative Affect Schedule

will be approximately 9 weeks (~3 weeks to complete arm 1, a 3 week break, ~3 weeks to complete arm 2).

Inclusion Criteria: 1) Age between 40-75 years, 2) movement-related deficit associated with first time middle cerebral artery stroke, 3) greater than 3-months post-stroke, 4) Fugl-Meyer score between 15 and 66 and 5) ability to elicit a motor evoked potential from the ipsilesional cortex.

Exclusion Criteria: 1) a score <23 on the Mini-Mental Status Exam, 2) a history of seizure/epilepsy, head trauma, major psychiatric diagnosis, neurodegenerative disorder or substance abuse, 3) a history of congestive heart failure, 4) systolic blood pressure above 120 mmHg and/or diastolic pressure above 80 mmHg, 5) the taking of any GABAergic, NMDA-receptor antagonist or other drug known to influence the neural receptors that facilitate neural plasticity, 6) an infarct resulting from ischemic stroke of anterior or posterior cerebral artery OR an infarct that encroaches within 2cm of the site of cTBS stimulation, 7) absence of an MEP in response to single pulse transcranial magnetic stimulation over ipsilesional M1 and 8) any other contraindication to TMS.

Behavioral Test Battery: Serial reaching task: Motor performance will be indexed with a serial reaching task (Aim 1) (Figure 2). This task was chosen as: 1) it involves a reaching motion similar to that emphasized during rehabilitation, 2) we can quantify the effects of dorsolateral prefrontal cortex stimulation upon procedural knowledge tied to larger movement sequences in addition to sensorimotor control of simple reaching and 3) we can assess declarative knowledge about the practiced task. We developed and have previously published with this task confirming it can be performed and learned by our prospective stroke patient participants.

Patients will perform reaches with their paretic arm between sequentially presented targets using a touch screen. Each target will appear once patients have come to a complete stop within the target for 500ms.

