Prior to each arm of the cross-over design patients will be informed of a repeated sequence of six targets that they will be required to reach to. Different sequences matched for difficulty will be used in each arm. Free recall will be performed prior to each session to assess any change in declarative knowledge.

During Sessions 2, 3, 4 and 5 of each cross-over arm participants will complete 30 reaches where the targets will occur in a random series. Participants will then complete a block of 60 reaches where the 6-element sequence will repeat 10 times. An additional block of 30 random reaches will then be completed. The pre-stimulation reaches will be used to assess sustained change in performance from session to session. This same set of 120 reaches will also be performed during Session 6 as a retention test.

For Sessions 2, 3, 4 & 5 participants will receive either active or sham cTBS over dorsolateral prefrontal cortex following the initial set of 120 reaches. Post-stimulation

[figure not shown]

Figure 2 – Serial Targeting task. Participants will be seated in front of a touch screen angled on a desk in front of them and be asked to touch sequentially presented targets using their paretic limb. Targets will be presented sequentially at one of nine locations (inset bottom left).

Study Title: Modulating interaction of motor learning networks in rehabilitation of stroke

participants will complete an additional 270 targeted reaches comprised solely of the 6-element repeating sequence.

The primary dependent measure for Aim 1 will be total response time to complete the sequence. As patients must stop within the target this metric captures both speed and accuracy. Comparison of response times during random reaches across session will be used to index sensorimotor procedural knowledge. Comparison of the difference between repeated and random reach response times will be used to index development of procedural knowledge relating to a larger sequence of movements.

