The statistical approach and power analyses were developed in consultation with the Center for Statistical Consulting and Research at the University of Michigan. For Specific Aim 1 (**Determine whether cTBS over contralesional dorsolateral prefrontal cortex prior to motor practice enhances motor learning post-stroke**) the primary outcome metric will be response time during random reaches. The extent of sensorimotor procedural knowledge will be assessed using an Arm (active-cTBS, sham-cTBS) x Session (Session 2, Session 6) repeated measures ANOVA. The extent of procedural knowledge relating to the larger movement sequence will be assessed using a Arm (active-cTBS, sham-cTBS) x Sequence (Random, Repeated) x Session (Session 2, Session 6) repeated measures ANOVA. As a secondary assessment, the rate of procedural learning will be assessed for each measure by including Sessions 3, 4 and 5 as levels of the factor Session. An Arm (active-cTBS, sham-cTBS) x Session (Session 1, Session 6) repeated measures ANOVA will be used to assess time to complete the Jebsen-Hand Function Test

For Specific Aim 2 (**Determine the effects of cTBS over dorsolateral prefrontal cortex upon motor networks**) two separate sets of analyses will be performed. First, separate Arm (active-cTBS, sham-cTBS) x Hemisphere x Time (Session 1, Session 6) repeated measures ANOVA will be performed to assess change in intracortical motor networks (recruitment curves, short-latency afferent inhibition) across study arm. Motor evoked potential amplitude will be the dependent variable. Arm x Hemisphere x Time interactions will be decomposed using separate Arm x Time repeated measures ANOVAs for each Hemisphere.

Second, to assess changes in intercortical neural networks group level maps for each identified component in the independent component analysis will be assessed using separate Arm x Sequence random-effects analysis for Session 1 and Session 6. Statistical threshold will be set to $p < 0.05$ and corrected for multiple comparisons using the false discovery rate.

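### The gap between random and repeated reaches is read as procedural knowledge although participants are told of the sequence, and the free recall that could show a declarative contribution enters no analysis

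*Combined protocol and SAP*

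**What the plan says.** All references are to the combined protocol and SAP.

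- **Disclosure.** Behavioral Test Battery: Serial reaching task states: "Prior to each arm of the cross-over design patients will be informed of a repeated sequence of six targets". Each arm uses a different sequence, matched for difficulty.
- **Recall.** The same section schedules a recall test: "Free recall will be performed prior to each session to assess any change in declarative knowledge". One of its three reasons for choosing the task is that "we can assess declarative knowledge about the practiced task".
- **Meaning given to the gap.** Still in that section: "Comparison of the difference between repeated and random reach response times will be used to index development of procedural knowledge", here for a larger sequence of movements.
- **Planned test.** Statistical Analyses and Power, Specific Aim 1: "The extent of procedural knowledge relating to the larger movement sequence will be assessed using a Arm (active-cTBS, sham-cTBS) x Sequence (Random, Repeated", crossed with Session (2 and 6) in a repeated measures ANOVA. As a secondary step, "the rate of procedural learning will be assessed for each measure by including Sessions 3, 4 and 5 as levels of the factor Session".
- **Primary outcome.** Statistical Analyses and Power says that "the primary outcome metric will be response time during random reaches". The serial reaching task section instead names total response time to complete the sequence as the primary measure.
- **Theory.** Potential Problems and Alternative Strategies describes consolidation of declarative and procedural knowledge as competitive, and says that suppressing dorsolateral prefrontal cortex during early consolidation could enhance procedural learning.

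**The concern.** A participant who knows the sequence can prepare the next reach in a repeated block but not in a random block. The speed advantage on repeated reaches can therefore contain explicit knowledge of what comes next as well as procedural skill. The plan gives the whole advantage to procedural knowledge. It collects the one measure that could show otherwise and states a purpose for it, but attaches no analysis.

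What is at stake is the interpretation of the Arm x Sequence x Session result. If active cTBS lowered recall, the gap could shrink and hide a procedural gain, or look like a procedural loss. If recall rose, the gap could widen and look like a procedural gain.

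**Working it through.** The plan gives no figure on this point to reproduce. The check is a comparison of sections, a short decomposition of the contrast, and one power calculation.

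**1. Is recall used anywhere?** The planned analyses, in Statistical Analyses and Power, are:
- random-reach response time, Arm x Session;
- response time, Arm x Sequence x Session;
- both of these again with Sessions 3 to 5 added;
- the Jebsen-Hand Function Test;
- motor evoked potential amplitude;
- resting-state component maps;
- the Aim 3 correlations with Fugl-Meyer score, motor evoked potential laterality, ipsilesional short-latency afferent inhibition and resting-state connectivity.

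Recall is not an outcome, covariate, mediator or check in any of them.

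**2. Can recall move the gap?** The next target appears only after a 500 ms stop in the current one. Someone who knows the order can use that interval to prepare. In a random series the order cannot be known, so this help reaches repeated reaches only.

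**3. What enters the three-way contrast?** Let D be random minus repeated response time in a given arm and session. The interaction estimates

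(D at Session 6 − D at Session 2, active) − (D at Session 6 − D at Session 2, sham).

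Write D = P + k × R, where P is the procedural part, R is the number of elements recalled, and k is the time saved per recalled element, taken as the same in both arms. The contrast becomes

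(arm difference in change of P) + k × (arm difference in change of R).

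- If recall is stable, or changes equally in both arms, the second term is zero.
- If recall changes differently, the second term is added to the first and carries the procedural label.
- If cTBS lowers recall and improves procedural skill, as a competition account would allow, the two terms have opposite signs.

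The documents give neither k nor any recall data, so the second term cannot be sized.

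**4. Does the timing fit?** In Sessions 2 to 5 stimulation follows the first 120 reaches. Session 2 recall and the Session 2 random and repeated blocks therefore precede the first stimulation of that arm. Session 6 recall follows all four stimulation sessions. Recall at Sessions 2 and 6 thus gives the same before-and-after contrast as the planned ANOVA.

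**5. Which outcomes are exposed?**
- The repeated-random gap: yes, by step 3.
- Total time to complete the sequence: yes, because it is measured on known targets.
- Random-reach response time: not directly, by step 2.

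**6. What could a recall test show with 16 participants?** Take the within-person arm difference in recall change, a paired two-sided test at 0.05, 15 degrees of freedom, and noncentrality d × √16 = 4d:

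| Standardized paired difference d | Noncentrality | Power |
|---|---|---|
| 0.3 | 1.2 | 0.203 |
| 0.5 | 2.0 | 0.465 |
| 0.75 | 3.0 | 0.801 |

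This assumes that all 16 complete both arms. A non-significant result would leave moderate recall differences open, so the estimate and its interval are needed.

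**The case against.** **The primary outcome is safe.** This stands for random-reach response time, which the statistical section names as primary. A reader might infer that the trial cannot support its mechanism at all. The documents do not support that: the sensorimotor index is not directly exposed, and Aim 1 is framed as motor learning and motor function. The protection is incomplete only because the task section names total sequence time as primary, and that measure is exposed. The two statements need reconciling in any case.

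**Explicit knowledge is the same in both arms.** Disclosure precedes each arm, so knowledge that is stable or equal does cancel. This narrows the point to a differential change. It does not remove it, because a differential change is what a prefrontal intervention could produce on the plan's own theory.

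**Recall may be near its ceiling.** Before Session 6 each participant has made 4 × (60 + 270) = 1,320 sequence reaches in the arm, or 1,320 / 6 = 220 repetitions. High recall in both arms is quite possible. The documents have no data either way, and the added analysis would show it.

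**Being informed may mean only being told that a sequence exists.** That reading is possible. Testing recall before every session fits disclosure of the content better, and on either reading participants know that there is a sequence to learn.

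**Recall may be considered informally.** Nothing says that it will be ignored. But a measure with a stated purpose and no analysis leaves that to discretion after the results are seen.

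Two further inferences should be resisted. A reader might put the bias at a fixed fraction of the gap per forgotten element; that would need the entire gap to be explicit recall, which is unknown. A reader might also suppose that the stimulation site was chosen for its part in declarative-procedural competition; the cTBS section instead cites earlier imaging of response after implicit learning.

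**Conclusion.** The point holds within limits. As planned, the Arm x Sequence x Session result cannot be attributed to procedural knowledge alone, because a between-arm difference in recall change would enter it unseen. The secondary learning-rate analysis of the same gap shares the weakness.

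The conclusion rests on two assumptions: knowing the order speeds repeated reaches, and cTBS could change recall differently from sham. Both are plausible from the task description and the stated theory; neither is shown by data in the documents. The size and direction of any distortion are unknown, and it is zero if recall changes equally in the two arms. The defect is one of interpretation and specification, and data already scheduled can address it.

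**What to change.** In Statistical Analyses and Power, Specific Aim 1:

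1. Define a recall score (elements recalled in the correct order, 0 to 6) and add an Arm x Session (2, 6) analysis of it. Report the arm difference in change with its confidence interval, and show the scores by arm and session so that a ceiling is visible.
2. Describe the Arm x Sequence x Session result as sequence-specific performance and interpret it alongside the recall result.
3. State that a non-significant recall test will not be taken to rule out a declarative explanation.
4. Do not adjust the main analysis for recall measured after stimulation has begun: it may itself be an effect of treatment, so adjustment would change the question being answered.

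The cost is one extra analysis of data already being collected and a narrower claim for the sequence-specific index. No added visit or measurement is needed.

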Targeted enrollment for Aim 1 (Behavior) and Aim 2 (Motor networks) is 16 participants. This number was derived using effect sizes from our previous work. We observed effect sizes (partial η^2) for two-way repeated measures Stimulation Site x Session interactions of 0.135 (M1-cTBS vs. Control) and 0.107 (S1-cTBS vs. Control) when comparing response time from early practice to a delayed retention test. Brodie et al. observed effect sizes for motor and sensory improvements pre- to post an S1-5Hz repetitive TMS intervention that ranged between medium (partial $\eta^2 = 0.06$) to large (partial $\eta^2 > 0.16$). Based upon these effect sizes, the targeted enrollment that provides a power of 0.80 at an alpha level of 0.05 with a correlation of 0.7 among the repeated measures is between 5 and 12 participants (G*Power). These numbers are consistent with previously published work using similar cross-over designs to investigate the efficacy of M1 non-invasive brain stimulation interventions upon both behavior and M1 physiology post-stroke (i.e. recruitment curves and short-latency- afferent inhibition). In these studies sample sizes range from 6-16 stroke patients. To

Study Title: Modulating interaction of motor learning networks in rehabilitation of stroke

account for effect sizes within the lower range of our estimates, overestimates of the correlations between the different levels in our repeated measures design as well as experimental mortality (see **Potential Problems and Alternative Strategies**), we will target 16 individuals.

With respect to the measures of resting state functional connectivity (Aim 2), the majority of work post-stroke has been aimed at determining differences in network functional connectivity compared to non-stroke control individuals. To our knowledge, no studies have assessed changes in resting state connectivity across an intervention similar to that proposed here. The closest approximation is a longitudinal study looking at functional connectivity between ipsilesional and contralesional M1 post-stroke. This study (n=12 patients) demonstrated significant differences between 1, 3 and 6 months post-stroke. Therefore, 16 individuals should be sufficient to detect any changes in functional connectivity associated with our intervention.

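### Aim 1 has two different primary outcomes: time to complete the sequence in the task section, random-reach response time in the statistical section

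*Combined protocol and SAP*

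**What the plan says.** The description of the serial reaching task (Behavioral Test Battery) tells patients about a repeated six-target sequence and separates it from random reaches. In Sessions 2 to 5, "participants will complete 30 reaches where the targets will occur in a random series". Next comes "a block of 60 reaches where the 6-element sequence will repeat 10 times", then a second random block of 30. The same 120 reaches serve as the retention test in Session 6.

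That section then says: "The primary dependent measure for Aim 1 will be total response time to complete the sequence". It continues: "As patients must stop within the target this metric captures both speed and accuracy". Only afterwards does it turn to random reaches, as an index that it does not call primary: "Comparison of response times during random reaches across session will be used to index sensorimotor procedural knowledge". A further index is the difference between repeated and random reaches.

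The Statistical Analyses and Power section says of Aim 1 that "the primary outcome metric will be response time during random reaches". The test follows: "The extent of sensorimotor procedural knowledge will be assessed using an Arm (active-cTBS, sham-cTBS) x Session (Session 2, Session 6) repeated measures ANOVA". Sequence-level learning is given a separate three-way ANOVA with reach type as the added factor, and this is not called primary. The sample-size paragraph takes effect sizes obtained "when comparing response time from early practice to a delayed retention test", and the Aim 3 correlations use change in response time. Neither says which reaches are meant.

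**The concern.** Both sentences are current text, both concern Aim 1 and both use the word primary, but they describe different data. The protocol also treats the two as different constructs: control of simple reaching on one side, knowledge of a longer movement sequence on the other. The choice therefore decides what a positive Aim 1 would mean.

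While both statements stand, either outcome could later be cited as prespecified. If the one that reached significance were reported as the primary, the 5% error rate would not hold. It would also be unclear which outcome the target of 16 was meant to serve. The text leaves this risk open; it does not show that such a choice is intended.

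**Working it through.** **1. Which reaches each statement covers.** Per test set, from the serial reaching task section:

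| | Random reaches | Repeated-sequence reaches |
|---|---|---|
| Count | 30 + 30 = 60 | 6 × 10 = 60 |
| Called primary in | Statistical Analyses and Power | Serial reaching task section |
| Arm × Session (2, 6) ANOVA given | Yes | No |

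The total is 120. The sentence just before the task section's primary statement describes post-stimulation practice made up only of the repeating sequence, so the repeated pattern is the natural meaning of *the sequence* there. On that meaning the two candidate outcomes share no reaches.

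**2. Does the sample-size calculation settle it?** The plan gives 5 to 12 participants for power 0.80 at alpha 0.05 with correlation 0.7. A repeated-measures noncentral F calculation with four within-patient cells and 1 and N − 1 df uses

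f² = η²/(1 − η²), λ = 4·f²·N/(1 − 0.7).

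| Partial η² | 0.06 | 0.107 | 0.135 | 0.16 |
|---|---|---|---|---|
| N required | 12 | 8 | 6 | 6 |

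This reproduces the upper end exactly. The lower end is 6 against the stated 5, and the plan's large effect is given as above 0.16, which would lower it further. Nothing in the calculation depends on reach type, so it cannot show which outcome is primary.

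**3. Error rate if either outcome could count.** With 16 patients, each Arm × Session (2, 6) interaction equals a paired t test on the between-arm difference of changes, with 15 df and critical |t| = 2.131. For two such tests,

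P(either significant) = 0.05 + 0.05 − P(both significant).

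At correlation 0 this is 1 − 0.95² = 9.75%. At other values P(both) depends on the correlation ρ between the two effects. The document does not give ρ, so a range is shown. The simulation is under no effect, with 1,000,000 runs per value and a Monte Carlo standard error of at most 0.03 points.

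| Assumed ρ | 0 | 0.3 | 0.5 | 0.7 | 0.8 | 0.9 | 0.95 |
|---|---|---|---|---|---|---|---|
| Simulated t tests, % | 9.69 | 9.51 | 9.14 | 8.44 | 7.94 | 7.16 | 6.58 |
| Bivariate normal approximation, % | 9.75 | 9.51 | 9.07 | 8.35 | 7.81 | 7.04 | 6.46 |

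The relative spread of the two measures has no material effect, because each t statistic is scale-free: at ρ = 0.7, SD ratios of 0.5, 1 and 1.5 give 8.5, 8.4 and 8.4%. The value 0.7 here is an assumption about the correlation between two effects. It is not the plan's 0.7, which is the correlation among repeated measures.

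**The case against.** The best defence is that the two sections answer different questions: the task section names the kind of measurement, and the statistical section says on which reaches it is taken. Several features support this.

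- The sentence after the task section's primary statement defends response time as a metric.
- The two indices that follow match the two ANOVAs of the statistical section, in the same order.
- No ANOVA is given for sequence time alone, so the random-reach outcome is the only stated primary with a matching test.
- The three-way ANOVA has a factor called Sequence with random as one of its levels, so the plan does not reserve the word strictly for the repeated pattern.
- The effect sizes behind the sample size come from two-way interactions, the form of the random-reach ANOVA.

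The objection adds that the inflated error rates need the literal reading, an analysis not in the plan, and selection after seeing results.

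Much of this stands. The milder reading is plausible, an analyst following the statistical section would have one outcome and one test, and the error figures are conditional. But the document does not state that reading or say that the statistical section governs. Time to complete the sequence does not describe reaches made to a random series. A two-way interaction fits either outcome equally well. None of these points makes the two sentences consistent.

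**Conclusion.** The concern holds. The plan contradicts itself on the Aim 1 primary outcome, and this must be settled before analysis because that outcome defines success.

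On the literal reading, with free choice between the two outcomes, the type I error would lie between 6.6% (ρ = 0.95) and 9.75% (ρ = 0), against a nominal 5%. Zero is the least plausible value, since both measures come from the same patients, task and sessions. At ρ = 0.7 to 0.9 the rate is about 8.4% to 7.2%. These figures assume an Arm × Session test on each outcome at two-sided 0.05, all 16 patients analysed, and success declared on either test. On the milder reading there is no inflation and only the wording needs correction. The three-way ANOVA is not counted as a competing primary, and this point does not challenge the target of 16.

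**What to change.** Before analysis, name one primary outcome for Aim 1 and one deciding effect, the Arm × Session interaction from Session 2 to Session 6. State both identically in the serial reaching task section and in Statistical Analyses and Power. The choice belongs to the investigators:

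- **Random-reach response time.** This is the simplest route, because its ANOVA is already there. Only the primary-measure sentence in the task section changes.
- **Sequence completion time.** Change the primary-outcome sentence in Statistical Analyses and Power, and add an Arm × Session ANOVA for this outcome.

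In either case, label the other reaching-task analyses secondary. State which response time the sample-size effect sizes and the Aim 3 correlations refer to.

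No new data are needed. One outcome loses its primary label, and the second route adds one ANOVA.

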Resting State Functional Magnetic Resonance Imaging: T2*-weighted blood-oxygen level dependent scans (single-shot EPI, TR=2000ms, TE=30ms, flip angle $\theta = 90^\circ$, FOV=220x220mm, voxel dimension=3.4x3.4x3.2mm, 40 slices, 10 min/scan) will be acquired during Session 1 and Session 6 of each study arm. During these scans patients will lay supine with their eyes fixed on a white cross presented upon a black background. Temporal correlations in spontaneous metabolic demand between neuroanatomical regions in the resting state infer task-related functional connectivity in healthy individuals and those post-stroke . Reductions in resting state functional connectivity have been demonstrated in motor networks within and across hemisphere post-stroke (for a review see) and are predictive of rehabilitation outcomes . Therefore, we will use resting state functional connectivity to quantify changes neuronal networks underlying procedural learning (Aim 2) and whether pre-intervention resting state functional connectivity within the motor network may predict intervention outcomes (Aim 3).

Study Title: Modulating interaction of motor learning networks in rehabilitation of stroke

Resting state data will be preprocessed as part of the standard processing stream at the University of Michigan that includes: removal of k-space outliers, field map corrections for inhomogeneity, removal of cardiac and respiratory rhythm, low pass filtering of data, slice time correction and motion correction (MCLIFRT, fMRIB software library) . Following pre-processing, the ARtifact detection tools (ART) toolbox will be used to identify global mean intensity outliers. An independent components analysis (Melodic, FSL) will be used to identify spatially distinct resting state networks including the motor, dorsal attention and default mode networks as well as any other networks that may be present.

Statistical Analyses and Power

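### The ART intensity-outlier check comes after low-pass filtering, which makes it less sensitive to brief, moderate artefacts in the resting-state scans

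*Combined protocol and SAP*

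**What the plan says.** The relevant text is in the section Resting State Functional Magnetic Resonance Imaging of the combined protocol and SAP.

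- Acquisition is given as "single-shot EPI, TR=2000ms, TE=30ms" and "40 slices, 10 min/scan", at Sessions 1 and 6 of each arm, so four scans per participant.
- The standard processing stream includes "removal of k-space outliers, field map corrections for inhomogeneity, removal of cardiac and respiratory rhythm", and then "low pass filtering of data, slice time correction and motion correction (MCLIFRT, fMRIB software library").
- The outlier check follows that stream: "Following pre-processing, the ARtifact detection tools (ART) toolbox will be used to identify global mean intensity outliers".
- The next step is the network decomposition: "An independent components analysis (Melodic, FSL) will be used to identify spatially distinct resting state networks".

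Under Statistical Analyses and Power, for Aim 2, "group level maps for each identified component in the independent component analysis will be assessed". Resting-state connectivity is also one of the four predictors listed for exploratory Aim 3.

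The filter type and cut-off, the ART threshold and what happens to a flagged volume are not stated.

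**The concern.** ART looks for volumes whose global intensity departs sharply from the rest of the series. A disturbance confined to one volume has its power spread evenly over all frequencies up to the Nyquist limit. A low-pass filter removes the upper part of that range, which cuts the height of the disturbance and spreads what is left over adjacent volumes. Background noise is reduced too, but by less, so the disturbance stands out less clearly. Placing the check after the filter works against its purpose.

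Artefact shared across voxels can appear as connectivity. What is at stake is precision in the imaging half of Aim 2 and in one Aim 3 predictor, with a target of 16 participants. Movement in the scanner is plausible: the protocol's own risk section expects discomfort from lying still, possibly made worse by post-stroke posture.

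**Working it through.** The plan gives no figure of its own to reproduce. The check takes two inputs from the document and varies the rest.

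**From the document.** Repetition time TR = 2 s, so the Nyquist limit is 1/(2 × 2) = 0.25 Hz. Scan length is 10 min, so 600/2 = 300 volumes.

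**Assumed, because the document is silent.** Cut-offs fc of 0.08, 0.10, 0.15 and 0.20 Hz; an ideal filter; a rule of |z| > 3 on the global mean; white background noise or lag-1 autocorrelation of 0.5.

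**Step 1: height kept.** An ideal low-pass filter keeps a fraction 2 × fc × TR of a one-volume spike. At 0.10 Hz this is 2 × 0.10 × 2 = 0.40. The first neighbour then carries sin(0.4π)/π = 0.30 of the original height. A zero-phase Butterworth filter gives almost the same values (0.41 and 0.28).

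**Step 2: z-score.** White-noise SD falls only to the square root of the fraction kept, about 0.64 at 0.10 Hz. The z-score is therefore multiplied by about 0.40/0.64 ≈ 0.63, and a 5-SD spike ends near 5 × 0.63 ≈ 3.2, close to the threshold. Autocorrelated noise loses less to the filter, so the z-score falls further.

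**Step 3: simulated detection of a single 5-SD, one-volume spike.** The range runs from autocorrelated to white background.

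| Series | Height kept | White-noise SD kept | Detected at \|z\| > 3 |
|---|---|---|---|
| Unfiltered | 100% | 100% | 97–98% |
| 0.15 Hz | 60% | 77% | 56–78% |
| 0.10 Hz | 40% | 64% | 22–52% |
| 0.08 Hz | 32% | 57% | 13–38% |

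**Step 4: where the loss shrinks.** All figures use the 3-SD rule and one event per scan unless stated.

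- A two-volume 5-SD event at 0.10 Hz is caught in 89–100% of series, and a three-volume event in 99–100%.
- A one-volume 10-SD spike at 0.10 Hz is caught in 94–100%.
- At 0.20 Hz 80% of the height is kept. With five spikes per scan, 6-SD spikes are caught in 90–95% of cases, against 99% unfiltered.

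**Step 5: where it grows.**

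- At 0.08 Hz with autocorrelated noise, a two-volume 5-SD event is caught in 76% of series and a one-volume 10-SD spike in 81%.
- With five spikes per scan and autocorrelation up to 0.8, detection of 10-SD spikes at 0.10 Hz is 63–93%.
- With a 5-SD rule and five spikes per scan, 8-SD spikes fall from 81–82% unfiltered to 0–1% at 0.10 Hz and to 39–50% at 0.20 Hz.

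The direction is fixed by TR and the stated order. The size depends on settings the plan does not give.

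**The case against.** The case on the other side has real force.

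- **Unstated settings.** Without the cut-off and threshold nobody can say how much detection is lost, and with a 3-SD rule and a cut-off near 0.20 Hz the loss is small. This stands, and it is why the figures are conditional.
- **An unfavourable example.** An isolated one-volume spike not far above the threshold is the artefact that filtering hides best. Movement that spans volumes is largely preserved. This also stands: the loss is concentrated in brief, moderate events.
- **Other safeguards.** Outliers in k-space are removed from the raw data first, and the independent components analysis may place some artefact in components of its own. Both may help. Neither is described as a whole-volume intensity check, and the plan adds ART for that purpose.
- **Same pipeline throughout.** All scans are processed alike within a person, so a missed artefact adds noise. It becomes bias only if artefact differs by arm or session, and nothing in the documents shows that it does.

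A reader might go further and infer three things that the text does not support. One is that ART will use global intensity alone: the plan names that measure but does not rule out others, and the list of steps is introduced as what the stream includes, not as complete. Another is that flagged volumes will be dropped one at a time, leaving the smeared remainder: the plan says only that outliers will be identified. The third is that many artefacts will be missed and will remain in the connectivity maps: that needs the unstated settings, and the calculation covers spike detection, not any effect on a component map.

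**Conclusion.** The concern holds in limited form. As written, the intensity-outlier check is applied to filtered data, and at TR 2 s this makes it less sensitive to brief, moderate spikes. The tabulated loss is substantial for cut-offs of 0.15 Hz or lower and rests on an assumed single 5-SD spike, 3-SD rule and ideal filter. Very large or longer events mostly survive under that rule; a stricter threshold would widen the loss.

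The consequence is possible extra noise in the Aim 2 resting-state maps and the Aim 3 connectivity predictor. The Aim 1 behavioural outcome and the sample size are unaffected. This is a low-cost improvement to a stated processing order, not a flaw that threatens the trial's main conclusion.

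**What to change.** In the resting-state section, run ART on the motion-corrected but unfiltered series. Flag volumes on global intensity and on the motion estimates that motion correction already produces, with the same thresholds for all four scans of a participant.

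Carry the flags forward. Before low-pass filtering and the independent components analysis, either model the flagged volumes with nuisance regressors treated consistently with the filter, or interpolate them. Do not simply delete them before filtering, because that breaks the even sampling an ordinary temporal filter assumes.

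State the cut-off, the ART thresholds and the handling of flagged volumes. The pre-processing list names filtering before motion correction. If that is the order of execution, the filter has to move later.

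The cost is a short protocol edit, a reordered script and slightly fewer effective volumes per scan. The stream is described as the university's standard one, so the change needs agreement with whoever maintains it. It requires no new data and adds no participant burden.
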